We hypothesize that the iLet BP will be non-inferior to the iPhone-based BP in dose administration and blood glucose control while subsequently improving user satisfaction with the device. We also hypothesize that Xeris glucagon in the iLet BP will be non-inferior to Lilly glucagon in the iLet BP in both infusion site reactions and occlusions.

In the Infusion Set Sub-Study, we hypothesize that the iLet infusion set will be non-inferior to the Contact Detach infusion set in plasma insulin levels, blood glucose control, and user experience.

The specific aims of this study are:

Aim 1. To conduct an outpatient study testing the safety and efficacy of the iLet BP versus our iPhone-based BP in up to 10 adult (≥ 18 years of age) subjects with type 1 diabetes in the fasted state, after a meal, and during and after exercise.

The study for this Aim will consist of two 8-hour study arms in random order: one with the iPhone-based BP and one with the iLet BP. Subjects will arrive fasting and remain fasted until the lunch meal. They will exercise on a stationary bike bpm for approximately 30 minutes with a heart rate from 120–140, starting at least 2 hours after lunch. The primary outcome will be the average percent dose amounts of both insulin and glucagon calculated by the control algorithm that are successfully delivered by the pump. Important secondary outcomes will include other metrics of device function (plasma insulin and glucagon levels will be measured every 30 minutes throughout the experiment) and measures of glycemic regulation, including mean CGM glucose and hypoglycemia exposure (% time <60 mg/dl).

Aim 2. To conduct an outpatient study testing the safety and efficacy of the iLet BP with Lilly glucagon versus Xeris glucagon in up to 10 adult (≥ 18 years of age) subjects with type 1 diabetes

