- After approximately 3-4 hours of closed loop control, the subjects will be permitted to eat lunch. The content of their meal will not be restricted in any way, with the exception that the number of carbohydrates should be in the "typical" range for them at lunch, and that they must eat the same meal at approximately the same time during both visits. Practically speaking, this means that they must have the same lunch that can be delivered or brought to the DRC. Subjects will select meals that will have a typical amount of carbohydrates for a lunch-time meal and will announce their meals to the bionic pancreas by selecting the "typical" option in the meal announcement screen.
- After lunch is completed, the subjects will not be allowed any carbohydrate intake (non-caloric drinks will be permitted) until the study is completed, to allow the bionic pancreas to control the post-prandial blood glucose without further interruption.
- Approximately 2 hours after lunch is completed (Hour 5-6 of the experiment), subjects will exercise on a stationary bike with a heart rate from 120-140 beats per minute (bpm) for a total of 4,000 heart beats (approximately 30 minutes). Subjects will rate their exercise intensity using the Borg scale every 5 minutes, with the target intensity level between 12 and 14. Heart rate will be measured every 5 minutes.
- BG measurements using the YSI will be obtained off of the IV line every 10 minutes during exercise. If the BG is < 80 mg/dl, BG measurements will be obtained off of the IV line every 5 minutes.
 - Carbohydrates will be given for any BG < 50 mg/dl according to the following protocol: Dextrose (g) = $BSA (m^2) / [1.7 m^2 (women) \text{ or } 1.9 m^2 (men)] * 15g$
 - Repeat treatments will be given at 15 minute intervals as long as BG remains < 50 mg/dl.
 - Heart rate will be measured every 5 minutes during exercise
 - Subjects will be asked to rate the intensity of their exercise every 5 minutes using the Borg Scale

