- Medical, surgical and social history, allergies and review of systems relevant to inclusion and exclusion criteria
- Medications (prescription and non prescription)
- Type of insulin used in pump
- Average total daily dose in the last 30 days (from pump history)
- Height and weight
- Blood pressure
- Urine HCG (pre-menopausal females)
- Hemoglobin
- Hemoglobin a1c

During Study Visits:

- Insulin analog given
- Basal rates for the duration of the experiment, and carbohydrate ratio and correction factor used for the meal bolus
- Timing and content of the meal eaten, including carbohydrate count
- Timing and amount of insulin dose given for the meal
- Plasma glucose levels at least every 30 minutes, more frequently in the low range
- Plasma insulin levels every 20-30 minutes (assayed with Mercodia Iso-insulin ELISA)
- Total insulin given throughout the experiment
- Timing and amount of any carbohydrates taken for hypoglycemia
- Infusion site assessments including pain, skin reactions, appearance of site, and any evidence of leaks
- Timing of any infusion site replacements
- Subject reports of symptoms of any other complaints
- User satisfaction with both infusion sets

VI. b. Study Endpoints

VI. b. 1. Primary endpoint analyses

Aim 1: This will be generated from the bionic pancreas data during each arm:

- Average percent dose amounts calculated by the bionic pancreas control algorithm that are successfully delivered by the pump (aggregate of both insulin and glucagon doses).

Aim 2:

This will be generated from the bionic pancreas data during each arm:

- Average percent dose amounts calculated by the bionic pancreas control algorithm that are successfully delivered by the pump (glucagon doses).

Aim 4: Insulin Area Under the Curve in the 3.5 hours following the insulin bolus

VI. b. 2. Secondary endpoint analysis – Infusion Set Sub-Study

- During the initial 90 minute fasted period:
 - AUC
 - Mean insulin levels
 - Difference between insulin levels at baseline and at 90 minutes
- After the insulin dose:
 - T_{max}
 - T_{½max}
 - C_{max}
 - AUC in the first 30 minutes
 - AUC in the first 60 minutes
 - AUC in the first 90 minutes
 - Terminal half-life
- Difference between the fasted PG value and the PG value at 90 minutes
- Difference in PG prior to the meal and peak post-prandial glucose
- PG AUC in the 3.5 hours following the meal
- Number of infusion sites replaced for clinically suspected failure
- Local skin reactions
- Infusion site pain

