- User satisfaction

VI. b. 3. Secondary endpoint analyses – Bionic Pancreas Function:

This will be generated from the bionic pancreas data during each visit:

- Average percent insulin dose amounts calculated by the bionic pancreas control algorithm that are successfully delivered by the pump.

- Average percent glucagon dose amounts calculated by the bionic pancreas control algorithm that are successfully delivered by the pump.
- Average percent dose amounts successfully issued to the pump by the bionic pancreas control algorithm that are successfully delivered by the pump (calculated doses are not issued unless the pump is accessible and its delivery channel is available).
 - Average percent insulin dose amounts successfully issued to the pump by the bionic pancreas control algorithm that are successfully delivered by the pump.
 - Average percent glucagon dose amounts successfully issued to the pump by the bionic pancreas control algorithm that are successfully delivered by the pump.
- Average percent dose amounts calculated by the bionic pancreas control algorithm that are successfully issued to the pump by the bionic pancreas (calculated doses are not issued unless the pump is accessible and its delivery channel is available).
 - Average percent insulin dose amounts calculated by the bionic pancreas control algorithm that are successfully issued by the bionic pancreas.
 - Average percent glucagon dose amounts calculated by the bionic pancreas control algorithm that are successfully issued by the bionic pancreas.
- Average percent of 5 minute steps during which the bionic pancreas is functioning nominally in all respects based on real-time CGM data (new CGM glucose reading captured, dose calculated, dose issued to pumps,
- Average percent of 5 minute steps during which the bionic pancreas is functioning nominally with or without a new CGM glucose reading captured (dose calculated, dose issued to pumps). If a CGM signal is not available, the dose calculated may be based on weight-based or historical basal rates.
- CGM reliability index, calculated as percent of possible values actually recorded by CGM.
- CGM MARD versus time-stamped BG values from YSI.
- List of technical faults associated with the bionic pancreas including cause and resolution.

VI. b. 4. Secondary endpoint analyses – Glycemic:

- All of following metrics will be generated from the DexCom G4 Platinum CGM data during each bionic pancreas visit.
 - Mean CGM glucose.

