The primary analysis of the designated endpoints will be calculated on an intention-to-treat basis. In cases where an arm was not completed (and that arm was not repeated according to protocol criteria) we will use the available data from that arm in the data analysis. We will only include arms that were started by the subject.

We will use the Shapiro-Wilk test to determine the normality of the residuals for each comparison and calculate percentages, means or medians, and standard deviation and/or ranges as appropriate in descriptive analyses. We will use paired t-test or the Wilcoxon signed rank test for comparison of means with normally or non-normally distributed residuals, respectively. In a secondary analysis we will look for any period effect and any interaction between treatment and period, although no such interaction is predicted for the primary outcome, and there is probably insufficient power to identify a small interaction.

VI. c. Power Analysis

The power analysis is based on data from previous studies using the iPhone-based BP. The following table shows the percentage of time that the insulin and glucagon pumps were available to deliver doses calculated by the bionic pancreas. When pumps were not available, this was typically due to loss of communication between the iPhone and the t:slim pumps, but could also be due to pump occlusion or inadequate drug in the reservoir, among many other possible reasons.

Table 1. Time that pumps were available in previous bionic pancreas studies

| Study | insulin | | Glucagon | |
|------------------------------|---------|-----|----------|-----|
| | Mean | SD | Mean | SD |
| Beacon Hill | 96.5 | 2.7 | 95.9 | 2.3 |
| Camp1 | 93 | 2.7 | 92.2 | 2.3 |
| Camp2 | 95.1 | 2.5 | 93.9 | 3.1 |
| Multi-center | 96.1 | 2.5 | 95.9 | 2.5 |
| Mean | 95.2 | 2.6 | 94.5 | 2.6 |
| Min | 93.0 | 2.5 | 92.2 | 2.3 |
| Max | 96.5 | 2.7 | 95.9 | 3.1 |
| ttest (insulin vs. glucagon) | | | 0.044 | |

The glucagon pump was unavailable a greater percentage of the time than the insulin pump in the iPhone-based BP. This could be due to more frequent reservoir changes (the glucagon reservoir had to be changed every day, while the insulin reservoir was changed every other day – the pumps were unavailable during the reservoir change process), greater number of occlusions in the glucagon tubing and infusion sets, or possibly other, unknown factors.

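### An incomplete arm that is not repeated enters the paired analysis on whatever was recorded, so a truncated Aim 4 AUC, a truncated cumulative total or a different mix of visit phases is set against a full visit

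*Combined protocol and SAP*

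**What the plan says.** The rule is in the analysis paragraph of section VI. b., just before VI. c. For an arm left incomplete and not repeated under the protocol's criteria, it states: "we will use the available data from that arm in the data analysis". It covers every designated endpoint, since "The primary analysis of the designated endpoints will be calculated on an intention-to-treat basis", and its only other limit is that "We will only include arms that were started by the subject". The tests are the paired t-test or the Wilcoxon signed rank test.

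The bionic pancreas visit (V. d. 4.) has a fixed order. "After approximately 3-4 hours of closed loop control, the subjects will be permitted to eat lunch"; exercise starts at Hour 5-6; the system is stopped after at least 8 hours. For the CGM endpoints, VI. b. 4. says "All of following metrics will be generated from the DexCom G4 Platinum CGM data during each bionic pancreas visit". VI. b. 5. adds totals and counts: insulin and glucagon delivered per kg, grams of carbohydrate, and numbers of episodes and interventions.

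The Aim 4 primary endpoint (VI. b. 1.) is "Insulin Area Under the Curve in the 3.5 hours following the insulin bolus". Under V. d. 5. the bolus is given at t=90 and the visit ends at t=300, which is exactly the end of that window.

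Provisions for repeating an arm vary:
- V. d. 4.: optional after a second CGM sensor failure or an unresolved device failure.
- V. d. 7.: optional when the function of the system or infusion set is in doubt, sub-study included; the ketone stop is rescheduled.
- V. d. 9. (site-reaction stops), withdrawals, and the discontinuations listed in IX. b.: no repeat is stated.

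**The concern.** Because the phases run in a fixed order, an early stop removes particular phases, not a random sample of time. The shortened visit is then paired with the same subject's full visit, and the difference mixes any device effect with the effect of unequal observation. For an AUC or a running total, the shorter visit is lower simply because it is shorter. For a time average, the two values describe different physiological states, and dividing by hours does not correct that.

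Two features make this more than a technicality. Several reasons for stopping (device failure, infusion-set failure, site reactions) relate to what is being compared, so truncation is unlikely to fall evenly across arms. And with about 10 pairs, one affected pair has a visible weight. In Aim 4, section VI. d. defines success as no significant difference, so added noise, or a shift against a true difference, works in favour of declaring success.

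**Working it through.** **The plan's own figures.** The documents give no number for incomplete arms. The only design calculation is the Aim 1 sample size of 25, 10 and 8. It is reproduced by n = 2(1.960 + 0.842)² × 2.5² / d², with d = 2.0, 3.2 and 3.6 points: 24.5, 9.6 and 7.6, rounded up. It does not depend on the incomplete-arm rule. Everything below rests on assumed values and is illustrative.

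**1. Aim 4 AUC.** The window is 300 - 90 = 210 min. Share observed at a stop T minutes after the bolus = AUC(0 to T) / AUC(0 to 210). The assumed curves are a flat profile (share = T/210) and one-compartment absorption curves with peak at 30-75 min, half-life 60-90 min, and an added constant baseline of 0 or 25% of peak.

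| Stop after bolus | Share of full AUC |
|---|---|
| 60 min | 25-46% |
| 90 min | 43-65% |
| 120 min | 57-79% |
| 150 min | 71-88% |
| 180 min | 86-95% |

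The low end at 120 min is the flat profile, 120/210 = 57%. The loss there is 21-43%.

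**2. One truncated AUC among 10 pairs.** Take a 40% loss.
- Shift of the mean paired difference: 40/10 = 4% of the AUC.
- Expected SD of differences, √(SD² + 40²/10): from an assumed 15% to √385 = 19.6%, or from 20% to √560 = 23.7%.
- 95% CI half-width, 2.262 × SD/√10: from 10.7 to 14.0, or from 14.3 to 16.9.
- By simulation, if the iLet set truly gave 20% less and one comparator-set AUC were cut by 40%, the chance of a significant difference falls from 96% to 66% (SD 15%) or from 80% to 47% (SD 20%).
- With no true difference, one such cut does not raise the false-positive rate (4.1% and 4.7%). The danger in this example is a masked deficit more than a false alarm.

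**3. Mean CGM glucose.** Assumed durations, from the V. d. 4. timetable: fasted 3.5 h, post-meal 2 h, exercise and after 2.5 h. With phase means f, p and e:
- full visit = (3.5f + 2p + 2.5e)/8
- stop at 3.5 h = f
- stop at 5.5 h = (3.5f + 2p)/5.5

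| f / p / e (mg/dl) | Full visit | Stop 3.5 h minus full | Stop 5.5 h minus full |
|---|---|---|---|
| 120 / 150 / 110 | 124.4 | -4.4 | +6.5 |
| 120 / 150 / 120 | 127.5 | -7.5 | +3.4 |
| 120 / 170 / 110 | 129.4 | -9.4 | +8.8 |
| 130 / 190 / 120 | 141.9 | -11.9 | +9.9 |
| 115 / 180 / 110 | 129.7 | -14.7 | +8.9 |
| 115 / 180 / 120 | 132.8 | -17.8 | +5.8 |

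Divided by 10 pairs, one affected subject moves the mean difference by -0.4 to -1.8, or by +0.3 to +1.0 mg/dl. No device effect is built in.

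**4. Other endpoints.** Totals per kg, carbohydrate grams and counts have no time denominator and are truncated directly. A stop before Hour 5-6 leaves no exercise endpoints. The Aim 1 and Aim 2 primaries are percentages of the calculated dose that was delivered; an early stop changes which doses enter the ratio but does not shorten it as it does an AUC. For Aim 2 it may leave few glucagon doses.

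**The case against.** The strongest reply is that the rule reaches only arms that were not repeated, and that device-related stops are the ones with repeat provisions. Section IV. a. also enrols up to 20 subjects so that up to 10 complete with a consistent protocol. This limits how often the problem arises, and no frequency can be derived from the documents. It does not remove the problem: most repeats are optional, several kinds of stop have none stated, and the rule applies to every started arm, not only to those of completers.

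It can also be said that the plan does not tell the analyst to enter a raw partial AUC as if it were the 3.5-hour value. True, but it names no alternative, so the choice would be made after the data are seen. The 30-, 60- and 90-minute AUCs often survive a stop, but they are secondary.

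A common window has its own weakness. It conditions on an event after randomisation, discards observed hours, and leaves the stopped arm's later course unseen. That stands, and is why the fix includes sensitivity analyses and a report of stops by arm.

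Three stronger readings are tempting and are not supported:
- *The failing system always looks better.* The sign depends on when the visit stops, as the glucose table shows.
- *Every hour after lunch is high, giving roughly -17 to -37 mg/dl for a stop at 3.5 h.* That gives exercise and recovery the post-meal mean, although the visit has a separate exercise phase.
- *Aim 1's fasted and post-meal questions are left unanswered.* Aim 1 names "in the fasted state, after a meal, and during and after exercise" as conditions of testing and then gives whole-visit outcomes; exercise has its own endpoints. Reporting by phase would be helpful but is not a missing requirement.

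**Conclusion.** The point holds within limits. As written, the rule pairs unequal observation periods whenever an arm is incomplete and not repeated. The most serious consequence is for the Aim 4 primary AUC, for stops between t=90 and t=300; a stop before t=90 leaves no primary value, and the plan does not say what happens then. Cumulative secondary endpoints are truncated likewise. The effect on mean CGM glucose is modest, below 2 mg/dl on the mean of 10 pairs for one affected subject, and can go either way. The Aim 1 and Aim 2 primaries and the stated sample sizes are largely untouched.

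The sizes rest on assumed insulin curves, SDs of differences and phase means, none of which the documents supply. The structural conclusion rests only on the fixed phase order, the fixed AUC window and the wording of the rule.

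**What to change.** Amend the analysis paragraph of VI. b. so that, for a pair with one incomplete and unrepeated arm:
- AUC, cumulative and time-averaged endpoints are computed in both visits over the elapsed time or sampling draws completed in both.
- The Aim 4 primary is the AUC from bolus to the last common draw, compared as a within-subject (log) ratio so that pairs with different windows can be combined. A stop before the bolus is treated as missing.
- All-available-data and completed-pairs-only results are given as sensitivity analyses.
- Early stops and their reasons are reported by arm, because a common window does not remove informative stopping.

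Optionally, summarise mean glucose and percent of time below 60 mg/dl descriptively by phase, to match the wording of Aim 1.

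The cost is analysis-plan wording and modest programming, with no new data, visits or subjects. The downside is that part of the complete visit goes unused in the main analysis of affected pairs, and that a ratio over a shortened window is not quite the same quantity as the full 3.5-hour comparison.

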- Once all of the results have been returned, a study MD will review the case report form to determine subject eligibility. If subjects are not eligible to continue in the study the results of abnormal tests will be reported to the subjects and to a health care provider of their choosing.
- Subjects who have been screened and are eligible can participate without having to be re-screened for a period of one year. The study staff should verbally confirm that there have been no health events that would make them ineligible if the interval between screening and participation is longer than 3 months.
- Subjects who participated in Aim 1 and/or Aim 2 will be eligible to participate in Aim 4, but will have to be rescreened if it has been more than 1 year.

V. d. 2. Visit Order: Once the subject has been enrolled and eligibility of subjects has been established, the order of the visits using Lilly glucagon with the iPhone based system and the iLet system will be randomized in blocks of two subjects. The experiments of Aim 2 (iLet BP with Xeris glucagon) will be performed after the first two visits.

The order of the visits for the Infusion Set Sub-Study of Aim 4 will be randomized in blocks of two subjects, separately from the visits for Aim 1 and Aim 2.

V. d. 3. Training Visit: A training visit will take place before the first bionic pancreas visit. Subjects will be

trained in the insertion and calibration of the Dexcom G4 sensor, insertion of infusion sets, use of the two bionic pancreas systems and study policies and procedures. Study staff will verify that the subjects have understood the material and are competent to participate safely in the study.

A training visit is not required for the Infusion Set Sub-Study.

V. d. 4. Bionic Pancreas Visits

- Up to 2 subjects may participate at the same time.
- Each subject will participate in the bionic pancreas visit three times: once with the iPhone-based BP, once with the iLet BP using Lilly glucagon and once with the iLet BP using Xeris glucagon.
- The night before the visit, subjects will place a Dexcom G4 CGM sensor that is provided by the study team, and calibrate the sensor when prompted using the provided Nova Biomedical Statstrip Xpress meter. Subjects will be instructed to call if they encounter any difficulty with their CGM.

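### The primary Aim 1 and Aim 4 comparisons leave out the randomised visit order, so a period effect, if there is one, costs power and, with unequal completers per order, biases the estimate

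*Combined protocol and SAP*

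**What the plan says.** Section V.d.2 (Visit Order) randomises the order of the two Aim 1 visits: "iPhone based system and the iLet system will be randomized in blocks of two subjects". Aim 4 has its own randomisation: "The order of the visits for the Infusion Set Sub-Study of Aim 4 will be randomized in blocks of two subjects". Aim 2 is different, because its order is fixed: "The experiments of Aim 2 (iLet BP with Xeris glucagon) will be performed after the first two visits".

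The closing paragraphs of section VI.b give the only method of comparison: "We will use paired t-test or the Wilcoxon signed rank test for comparison of means with normally or non-normally distributed residuals, respectively". Neither test contains a period or sequence term. Period is mentioned once more: "In a secondary analysis we will look for any period effect and any interaction between treatment and period". No model is given for that step, and no consequence for the primary result is stated. The plan predicts no treatment-by-period interaction for the primary outcome and concedes that "there is probably insufficient power to identify a small interaction".

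Section IV.a allows up to 20 enrolled subjects for up to 10 completers and expects that some experiments may stop early. No rule keeps completers balanced by order.

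**The concern.** In a two-period crossover, a general shift from visit 1 to visit 2 enters the within-subject differences with opposite signs in the two orders. If the orders are equal in size, the shift cancels from the mean but inflates the variance of the differences, so the paired test loses power. If they are unequal, part of the shift stays in the treatment estimate.

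A shift is plausible, though not shown. This is the first human use of the iLet (section I.d), subjects are newly trained on both systems (V.d.3), and staff help with set-up and troubleshooting (V.d.4). The prediction of no interaction does not answer the point, because a period effect common to both devices is not an interaction.

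The power calculation in VI.c arrives at 10 subjects with no allowance for a period effect. The loss of power also matters where success means finding no significant difference, as for the glycemic measures in Aim 1 and infusion set performance in Aim 4 (VI.d). In those comparisons a less sensitive test makes success easier to declare.

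**Working it through.** **Inputs from section VI.c.** iPhone system 96%; iLet 98%, 99.2% or 99.6%, so differences of 2.0, 3.2 and 3.6 points; SD 2.5 in each arm; two-sided alpha 5%; power 80%. The documents give neither a within-subject correlation nor a period effect. Both are assumed below.

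**The plan's own figure.** n = 2 × 2.5² × (1.960 + 0.842)² / difference² gives 24.5, 9.6 and 7.6, rounded up to 25, 10 and 8, as stated. This is a normal approximation. It corresponds to pairs with correlation 0 and no period effect.

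**Model.** Let δ be the treatment difference (iLet minus comparator) and π the shift, visit 2 minus visit 1. The within-subject difference has mean δ + π when iLet comes second and δ − π when it comes first. With correlation 0 its SD is 2.5 × √2 = 3.54.

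**Balanced completers, 5:5.** The paired mean is unbiased. The expected variance of the differences rises from 12.5 to 12.5 + π² × 10/9. Power at δ = 3.2, by simulation:

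| Shift π (points) | Paired t, 9 df | Period-adjusted, 8 df | Paired type I error |
|---|---|---|---|
| 0 | 72% | 71% | 5.0% |
| 1 | 69% | 71% | 4.1% |
| 2 | 60% | 71% | 2.6% |

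The two powers cross at a shift of about 0.6 points; below that the paired test is equal or slightly better. With an assumed correlation of 0.5, paired power is 95%, 92% and 84%, against 94% adjusted.

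**Unbalanced completers.** Bias of the paired mean = π × (n with iLet second − n with iLet first) / n.
- 6:4: (6 − 4)/10 = 0.2, so the bias is ±0.2π, or 0.4 points at π = 2.
- 7:3: (7 − 3)/10 = 0.4, so the bias is ±0.4π, or 0.8 points at π = 2.

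The period-adjusted estimate is unbiased in both cases.

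**How the adjustment must be coded.** Take six subjects with iLet second, four with iLet first, δ = 3.2 and π = 2. The order-specific means are 5.2 and 1.2.
- Paired mean: (6 × 5.2 + 4 × 1.2)/10 = 3.6. A regression on sequence centred at its sample mean has this same value as its intercept.
- Average of the two order means: (5.2 + 1.2)/2 = 3.2, the true value. Coding sequence as +1/2 and −1/2 gives this intercept.

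**Cost when there is no shift.** Adjusted SE = (3.54/2) × √(1/n₁ + 1/n₂), on 8 df (critical value 2.306 instead of 2.262). The paired test has SE 1.12 and power 72%.
- 5:5: SE 1.12, power 71%, interval about 2% wider.
- 6:4: SE 1.14, power 69%, interval about 4% wider.
- 7:3: SE 1.22, power 63%, interval about 11% wider.

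**The case against.** The strongest reply is that the effect is probably small for Aim 1. The endpoint cannot exceed 100% and the iLet is planned at 99.2%. A 2-point shift spread evenly round that mean would put the two visits at 98.2% and 100.2%, which is impossible; the largest such shift is 2 × 0.8 = 1.6 points. Section VI.c attributes most past unavailability to lost communication between phone and pumps, which is not obviously a learning effect, and training on both systems comes before the first visit. This stands. It makes the 2-point row an upper extreme and leaves about 2 points of power at a 1-point shift.

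The margin from 20 enrolled to 10 completers also does not by itself show imbalance. Part of it is screen failures, and order is assigned only after eligibility is confirmed. Blocks of two keep allocation near 1:1, and repeating failed arms helps to retain pairs. What remains is dropout after randomisation, which the plan anticipates without stating a rate.

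A reader might infer that the plan ignores period altogether, or that false-positive findings become common. The documents support neither. A secondary look at period is planned. With balanced orders the paired test becomes conservative. In the simulations its type I error stays below 5% at 6:4 when a shift is present and reaches only about 5.4% to 6.7% at 7:3 with shifts of 1 to 3 points.

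For Aim 4 there is no power calculation, and basal rates, insulin dose and meal are the same at both visits. No size can be given there, but the structural argument is the same.

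**Conclusion.** The point holds as a modest, inexpensive improvement for Aims 1 and 4. The order is randomised and recorded, yet the primary estimate does not use it, and the planned secondary look does not feed back into that estimate.

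Its size depends on a period effect that the documents do not quantify. At 5:5 and correlation 0, the paired test gives up about 2 points of power to the adjusted analysis at a 1-point shift and about 11 at the extreme of 2 points; below about 0.6 points it gives up nothing. Bias arises only if completers are unequal by order, and then equals 20% of the shift at 6:4 and 40% at 7:3.

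It would go too far to conclude that the planned test is invalid or that its result would be biased as a matter of course: that needs both a real shift and unequal orders. Nor does the point extend to Aim 2. With Xeris always last, treatment and period are largely confounded, and a period term cannot separate them.

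**What to change.** In section VI.b, make the primary analysis for Aims 1 and 4 period-adjusted and report the estimate with a 95% confidence interval. Either form will do:

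- the average of the two order-specific mean differences, obtained by regressing the within-subject difference on sequence coded +1/2 and −1/2, and explicitly not centred at the sample mean; or
- a mixed model with treatment, period and subject.

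Where residuals are non-normal, use a rank-sum test comparing the within-subject period differences (visit 2 minus visit 1) between the two orders. This keeps a non-parametric option for a percentage close to its ceiling. Retain the planned paired t or signed-rank test as a sensitivity analysis.

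The change is to the analysis wording only; no new data are needed. The price is one degree of freedom. If there is no period effect, power falls by about 1 point at 5:5, 3 points at 6:4 and 9 points at 7:3 under the planning values above. Leave Aim 2 out of this change.
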